## 9.4.6 SUB-GROUP ANALYSES

We will include sex as a covariate in the statistical models, as well as explore possible interactions between sex and other independent variables, to identify any sex-based differences in the relationship between exercise volume load and the net head acceleration outcome.

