## 4.2 SCIENTIFIC RATIONALE FOR STUDY DESIGN

The control exercise group will perform only "shoulders-down" resistance exercises not directly targeting the neck so that the effects of the high intensity neck exercise program can be distinguished from changes associated with normal age-related growth and development or generalized effects of resistance training not specifically targeting the neck.

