## 4.3 JUSTIFICATION FOR DOSE

All subjects will exercise 2 days per week under the direct supervision of a study-assigned strength coach (National Strength and Conditioning Association Certified Strength and Conditioning Specialist, CSCS, certification), with a minimum of 1 day of rest between exercise sessions. Subjects will be assigned either to a high intensity neck strengthening exercise group or to a control exercise group performing only "shoulders-down" resistance exercises not directly targeting the neck. All exercises will be performed in accordance with National Strength and Conditioning Association standards. The neck strengthening program will include manual resistance exercises in sagittal-plane flexion and extension, coronal-plane lateral flexion to the left and right, and axial-plane rotation to the left and right, as well as dumbbell shoulder shrugs as previously described by our group. For each group, the exercise program

will progress in volume and intensity over the duration of the study, to accommodate muscular fitness adaptation. Such progression is considered vital to the long-term efficacy of resistance exercise programming.

The volume load of neck strengthening exercise will be calculated using a modified protocol previously employed by our group for the elbow flexors. For shoulder shrugs the volume load for each exercise session will be defined as the product of the dumbbell weight x the force of gravity (g= 9.8 m/s2) x the number of repetitions performed during the exercise session, to yield a volume load for the exercise session in N. During manual resistance exercise, the strength coach will hold a hand-held dynamometer against the subject's head to measure and record the force applied during manual resistance. For both dumbbell shrugs and manual resistance exercises, the total cumulative exercise volume load will be defined as the sum of the individual session volume loads over all exercise sessions completed by the subject. Since subjects assigned to the control group will not perform neck strengthening exercise, their exercise volume load will remain zero throughout the study.

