#### 6.2 MEASURES TO MINIMIZE BIAS: RANDOMIZATION AND BLINDING

Subjects will be randomized using a centralized electronic randomization tool with equal allocation to the control and high-intensity neck strengthening groups. Balanced block randomization will be used to ensure equal sex and age category balance between the groups. Age category will correspond to high school under-class (i.e., age 13.0 - 16.49 years at the time of randomization) vs. upper-class (i.e., age 16.50 – 19.99 years) status given the typical maturation occurring in adolescents through the high school years. Subjects will be considered enrolled in the trial upon randomization and available data will be included in the intention to treat analysis. The Study Statistician, Strength Coach, Study Coordinator, and PI (or his Co-I designee when necessary to make a determination of AE relatedness to the study) will not be blinded to subject group allocation. Other members of the study team, including those responsible for performing the laboratory- and radiology-based assessment will be blinded to group allocation status. Subjects will not be informed of their group allocation status, although they will be aware of whether or not they are performing neck strengthening exercises during their exercise sessions. Subjects will be instructed not to discuss whether they are performing neck strengthening exercises during their exercise sessions.

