## 9.2 SAMPLE SIZE DETERMINATION

Our power calculation is based on AIM 1. Assuming net head acceleration (on the logarithmic scale) will follow linear trends over time, then our power calculation is based on comparison of the slope of this change, which has 9/14 of the variance, i.e., 36% less variance, than the underlying log(net head acceleration) measurements. As a result, the standardized effect size (Cohen's d value) of the slope is approximately 1.25 times greater than that of the underlying log(net head acceleration) measurements. Based on our own pilot data, we expect observed standardized effect sizes to be between .6 and 1.0 for log(net head acceleration), depending on the variability of the individual measurements across the 4 directions of motion. These values correspond with a 20% overall reduction in un-transformed net head acceleration. A total of 30 subjects in each exercise group (control and high intensity), will provide power of between .83 [for standardized effect size for log (net head acceleration) of .6 and 1.0 [for standardized effect size in the population. To account for the possibility of a drop-out rate of up to 20%, we will plan to enroll up to a total of 72 subjects.

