## 9.4.2 ANALYSIS OF THE PRIMARY AND SECONDARY EFFICACY ENDPOINTS

We expect a percentage reduction in net head acceleration as the volume load of exercise performed increases over the 12 week exercise program, so we will assess net head acceleration on a logarithmic scale to allow us to model and detect a constant change. For example, a 20% reduction in net head acceleration corresponds to a difference of log(.8) on the log-scale, regardless of the initial value of net head acceleration. We will use linear mixed models to describe the longitudinal changes in log(net head acceleration) over the volume loads of exercise performed at each of the four study time points, and to test the significance of this change across the three exercise groups.

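### Age category is a randomisation factor but no model includes it; precision is forgone if age affects the level of, or the change in, head acceleration

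*Combined protocol and SAP*

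**What the plan says.** Section 6.2 (Randomization and Blinding): "Balanced block randomization will be used to ensure equal sex and age category balance between the groups". The age category splits at 16.5 years (13.0–16.49 against 16.50–19.99 at randomisation), and the reason given is "given the typical maturation occurring in adolescents through the high school years".

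Section 4.2 says that the control arm is there so that the exercise effect "can be distinguished from changes associated with normal age-related growth and development".

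Section 9.4.2 gives the primary and secondary model: "We will use linear mixed models to describe the longitudinal changes in log(net head acceleration) over the volume loads of exercise performed". It lists no covariates and no random effects, and names neither a separate time term nor a group main effect. Section 9.4.6 (Sub-Group Analyses) adds: "We will include sex as a covariate in the statistical models". That sentence can be read as covering 9.4.2. The exploratory models in 9.4.8 name no age term. Age could enter only among the demographics compared at baseline in 9.4.4.

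Section 9.2 says that "our power calculation is based on comparison of the slope of this change". Sections 1.1 and 3, by contrast, define the primary endpoint as a value at Assessment Time Point 4.

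**The concern.** The trial names two factors important enough to balance allocation on, and then carries one of them into the analysis. Balancing on a prognostic factor makes the group estimate more precise, but the analysis shows this only if the factor is in the model. Otherwise the age variation stays in the error term, the reported standard error is too large, and a real effect is harder to detect than it need be.

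The protocol treats maturation as relevant twice: as the reason for the age category, and as the change over time that the control arm has to absorb. At stake is some power in a trial planned for .83 at the low end of its effect range, together with an adjustment choice that should be fixed before the data are seen.

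**Working it through.** **1. The plan's own figure.** From 9.2: 30 per group, d = .6, slope multiplier 1.25; from 9.4.1: alpha .05 (two-sided assumed). Slope effect = .6 × 1.25 = .75. Power = Φ(.75 × √15 − 1.96) = Φ(2.905 − 1.96) = .828, which matches the stated .83. A noncentral t gives .815. No age adjustment enters this figure.

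**2. Age affects level only.** Generalised least squares was used with a random intercept, four equally spaced visits, 30 per arm, sex in the model and age balanced. Within-person correlation and the R² for age are assumed.

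- Group, time and group by time: the standard error of the slope difference is unchanged (ratio 1.000) with age in or out. The same holds for a volume-load model with a group main effect.
- Models without a group main effect: including age cuts the standard error by 0.1% to 2.5% (correlation .7 to .9, R² .05 to .20). Type I error with age omitted is .046 to .050.
- Comparison at Assessment 4, 30 per arm, d = .6, half the athletes in each category: .6 × √15 = 2.324. An age difference of a SD explains R² = a²/4. Power with age omitted is Φ((2.324 − 1.96)/√(1 − R²)); with age included it is Φ(2.324/√(1 − R²) − 1.96).

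| Age difference (SD) | R² | Power, age omitted | Power, age included |
|---|---|---|---|
| 0.25 | .016 | .643 | .649 |
| 0.5 | .0625 | .646 | .670 |
| 0.8 | .16 | .654 | .718 |

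**3. Age affects change over time, random-slope model.** With complete balanced data this is a t-test on subject slopes, with sex in the model. Balanced allocation removes age from the group difference, so the true variance is proportional to 1 − R², while the model without age uses about 1. Including age cuts the standard error by 1 − √(1 − R²). Type I error with age omitted is approximately 2(1 − Φ(1.96/√(1 − R²))). The power columns, at slope effect .75, come from simulation with 400,000 replicates.

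| Slope R² for age (assumed) | SE cut | Type I error, omitted | Power, omitted | Power, age by time included | Forgone (points) |
|---|---|---|---|---|---|
| 0 | 0 | .050 | .815 | .815 | 0 |
| .05 | 2.5% | .044 | .819 | .833 | 1.4 |
| .10 | 5.1% | .039 | .826 | .853 | 2.7 |
| .15 | 7.8% | .034 | .832 | .873 | 4.1 |
| .20 | 10.6% | .028 | .838 | .890 | 5.2 |

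With age by time included, simulated type I error is .049 to .050. A 2:1 age split gives the same results to within .002.

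**4. Random intercept only.** Section 9.4.2 does not say which random effects are used. With age at 10% of slope variance and no other slope differences between athletes, type I error with age omitted is about .045. If other slope heterogeneity is 20%, it is .065 omitted and .072 included; at 40% it is .091 and .100. The missing random slope causes this inflation, not age.

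**5. Where balance does not protect.** These cases assume 36 per arm, a constant age difference of 1 SD, within-person correlation .3, .5 and .8, and group and time in the model.

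- Differential dropout (10 older treated and 4 younger control athletes leave after the second visit): the slope shifts by −.054, −.033 and −.011, against standard errors of .095, .081 and .052.
- Regression on achieved load, older treated athletes lifting 1.25 times the load: the coefficient shifts by .042, .023 and .007, against .077, .065 and .041. With equal loads the shift is 0.

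**The case against.** The strongest reply is that nothing is broken. The plan is silent on age and does not exclude it, and allocation already removes age from the group difference. In the random-slope figures, power with age omitted rises from .815 to .838 as the age share grows, so it never falls below the case without an age effect. That stands: the 1.4 to 5.2 points are forgone, not lost against .83.

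It is also fair that the documents give no size for an age-by-time effect. Section 4.2 says that growth occurs during the study, not that it differs between the two age categories over 12 weeks. The reason given in 6.2 supports a difference in level at least as well as one in slope. Every non-zero figure is therefore conditional.

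Three stronger readings are tempting, and the documents do not support them.

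- **That only age by time is missing.** This holds for a group-by-time slope with a free intercept per group and complete data. The plan regresses on achieved volume load, keeps partial data (9.3) and defines the primary endpoint at Assessment 4, so the main effect matters too.
- **That the test is always conservative without age.** This is secure for the random-slope model only; step 4 shows the opposite for a random intercept with other slope heterogeneity.
- **That omitting age biases the trial, or that it cannot.** With complete data and loads unrelated to age there is no bias. The plan guarantees neither, but the shifts in step 5 rest on invented patterns, and each is smaller than its standard error.

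**Conclusion.** The point holds as an optional improvement. Age category is used to allocate and is then named in no model. The randomised comparison remains valid and the .83 stands without age.

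The cost of omission depends on how age acts. An effect on level costs nothing for a group-by-time slope, up to 2.5% of the standard error in the models examined without a group main effect, and some power at Assessment 4 (.654 against .718 at an assumed 0.8 SD difference). An effect on change gives a type I error of about .044 to .028 and forgoes about 1.4 to 5.2 points of power, for an assumed 5% to 20% of slope variance. With no age effect the cost is nil.

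The slope figures assume a random-slope model, complete data, 30 per arm and d = .6. They do not carry over to a random-intercept-only model.

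**What to change.** In 9.4.2, state that the primary and secondary mixed models include:

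- an explicit time term;
- both randomisation factors as fixed effects: sex, and age category (13.0–16.49 against 16.50–19.99 years at randomisation);
- age category by time;
- a subject-level random slope.

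Keep the sex interactions of 9.4.6 exploratory.

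The cost is one sentence and a few degrees of freedom. With linear time, age category takes one and age category by time one. With categorical time over four visits the interaction takes three. The time term itself is extra, because 9.4.2 does not name one now. No new data are needed, since age category is recorded at randomisation.

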## 9.4.7 TABULATION OF INDIVIDUAL PARTICIPANT DATA

N/A

## 9.4.8 EXPLORATORY ANALYSES

We will construct linear models with net head acceleration as the outcome and combinations of neck strength and/or cervical muscle volume as the predictor(s) for direct and indirect force application under both the anticipated and unanticipated conditions. Rather than comparing the B coefficients of the neck strength and cervical muscle volume terms, which are scale-dependent, we will instead quantify the impact of each cervical covariate on net head acceleration by calculating the differences in  $R^2$  values of statistical models with vs. without each cervical variable. These differential  $R^2$  values indicate the importance of each cervical variable in the model, accounting for the other. There is no known analytic solution in the statistical literature to confirm statistically whether one differential R^2 value is higher than the other unless the null hypothesis is zero differential R^2, which is not the case here. Instead, we will use the bootstrap as a nonparametric tool to assess the variability in the differential R^2 values. By bootstrapping the subjects a sufficient number of times, we can obtain a set of differential R^2 values and use them to construct 95% confidence intervals around the differential R^2 values of both cervical variables during the anticipated and unanticipated conditions. If the confidence intervals are non-overlapping, we will conclude that the cervical variable associated with a greater decline in R^2 value upon its removal from the full model is significantly more impactful on the net head acceleration for the given anticipation condition.

We will compare the magnitudes of the B coefficients associated with each cervical independent variable at each time point in the linear mixed model analyses predicting log(net head acceleration). The effect of neck strengthening exercise on the exploratory net head acceleration during soccer heading outcomes will be analyzed using a similar statistical analysis plan as described above in Section 9.4.2.

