Objectives:		Primary Objective (AIM 1): To determine the effect of manual resistance neck strengthening exercise on net head acceleration during simulated sport-associated impacts to the head (direct loading condition). Secondary Objective (AIM 1): To determine the effect of manual resistance neck strengthening exercise on net head acceleration during simulated sport-associated impacts to the body (indirect loading condition). Exploratory Objective (AIM 1): To determine the effect of manual resistance neck strengthening exercise over time on neck strength, cervical muscle volume, neuromuscular recruitment, and net head acceleration under direct and indirect loading as well as during voluntary soccer heading. Exploratory Objective (AIM 2): To determine the relative influences of baseline neck strength and cervical muscle volume on net head acceleration during simulated sport-associated impacts to the head and body with and without volitional, anticipatory cervical muscle pre- contraction to brace for the impact.

Endpoints:	Primary Endpoint: Mean area under the net head acceleration vs. time curve during direct loading, with anticipatory bracing, at Assessment Time Point 4.
	Secondary Endpoint: Mean area under the net head acceleration vs. time curve during indirect loading, with anticipatory bracing, at Assessment Time Point 4.
Study Population:	Up to 72 male and female high school soccer athletes in and around Ann Arbor Michigan.
Phase:	N/A
Description of	University of Michigan.
Sites/Facilities Enrolling	
Participants:	
Description of Study	Neck strengthening resistance exercise.
Intervention:	
Study Duration:	Approximately 60 months.
Participant Duration:	Approximately 4 months.

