The premise that neck strength and cervical muscle volume may exert differential influences on head acceleration during anticipated vs. unanticipated impacts is further supported when considering each potential cervical contributor to head acceleration. Previous work concluded that since the mechanical properties of the neck's non-contractile tissues (e.g., bone, ligament) are not affected by muscle activation, and because peak head acceleration is reached before either a reflexive or voluntary muscular response has had time to occur, head acceleration is primarily influenced by the mechanical properties of the cervical muscles. Passive muscle stiffness is strongly influenced by the amount of muscle tissue being acted upon. In contrast, the stiffness of actively contracting muscle increases proportionally with muscle activation and torque. Therefore for any volume of cervical muscle, greater neck strength (i.e., torque generation) associated with improved neuromuscular recruitment is expected to confer greater muscle stiffness during maximal anticipatory cervical muscle pre-contraction to brace for the impact. While muscle strength and volume co-vary, these characteristics are known to change independently from one another with aging, disuse, and of greater direct applicability to this proposal, following resistance training. There remains a knowledge gap in how individual cervical muscle attributes affect head acceleration during sport-associated impacts with vs. without anticipatory cervical muscle pre-contraction to brace for the impact.

AIM 2 will directly address this knowledge gap by comparing the relative weights of neck strength and cervical muscle volume in predicting net head acceleration during anticipated and unanticipated impacts to the head and body.

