Exploratory Objective 2 (AIM 2):	activation, antagonist muscle	cervical muscle volume and
To determine the effect of	inhibition based on surface	activation patterns. This study
manual resistance neck	EMG); mean area under the net	also seeks to determine the
strengthening exercise on the	head acceleration vs. time curve	relative influence of neck
relative influence of neck	during direct and indirect	strength vs. cervical muscle
strength vs. cervical muscle	loading, with anticipatory	volume on head acceleration
volume on net head	bracing, at Assessment Time	during impacts to the head and
acceleration during direct and	Points 1, 2, 3; mean area under	body that are anticipated (i.e.,
indirect loading with and	the net head acceleration vs.	with bracing) vs. unanticipated
without volitional, anticipatory	time curve during voluntary	(i.e., without bracing), and will
cervical muscle pre-contraction	soccer heading at Assessment	explore whether the relative
to brace for the impact.	Time Points 1, 2, 3, 4.	influence of neck strength vs.
	Exploratory AIM 2 Endpoints:	cervical muscle volume on head
	Mean area under the net head	acceleration is influenced by
	acceleration vs. time curve	manual resistance neck

OBJECTIVES	ENDPOINTS	JUSTIFICATION FOR ENDPOINTS
	during direct and indirect	strengthening exercise. In
	loading, without anticipatory	addition to the direct and
	bracing, at Assessment Time	indirect loading conditions,
	Points 1, 2, 3, 4.	which are both passive (i.e.,
		force application is not initiated
		by the subject), voluntary
		soccer heading is also included
		as an exploratory loading
		condition representing a more
		active sport-associated impact
		scenario.

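### AIM 2 is worded two ways, and Section 9.4.8 states no between-arm contrast for the version that asks whether exercise changes the relative influence of neck strength and muscle volume

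*Combined protocol and SAP*

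**What the plan says.** Three places describe AIM 2.

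- Section 1.1 (synopsis) sets the exploratory objective "To determine the relative influences of baseline neck strength and cervical muscle volume on net head acceleration", with and without bracing. No exercise effect is mentioned.
- Section 2.2 agrees in substance: AIM 2 fills its gap by "comparing the relative weights of neck strength and cervical muscle volume in predicting net head acceleration during anticipated and unanticipated impacts".
- Section 3, read across the broken table columns, makes the objective the effect of manual resistance neck "strengthening exercise on the" relative influence of the two attributes, with AIM 2 endpoints at Time Points 1 to 4. Its justification column carries both questions: it seeks the relative influence, and will also "explore whether the relative" influence is altered by the training.

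The analysis is in Section 9.4.8. Its first paragraph reads "We will construct linear models with net head acceleration as the outcome and combinations of neck strength and/or cervical muscle volume as the predictor(s", for each loading and anticipation condition. It computes the loss in R-squared when each attribute is dropped and bootstraps subjects for 95% intervals. If the intervals do not overlap, it declares that one attribute "is significantly more impactful on the net head acceleration for the given anticipation condition". The second paragraph adds: "We will compare the magnitudes of the B coefficients associated with each cervical independent variable at each time point in the linear mixed model analyses" of log(net head acceleration).

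**The concern.** The synopsis question is an association among athletes before training. The Section 3 question is a randomised effect: does assignment to neck training change how much strength matters relative to volume? The second needs a comparison between arms, and none is written down.

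The control group exists, by Section 4.2, so that the effect of neck exercise can be told apart from adolescent growth and from resistance training in general. A shift from Time Point 1 to Time Point 4 with the arms combined gives up that protection. A report that training moved control of the head from volume towards strength, or the reverse, would then not rest on randomisation. Because Section 9.4.8 does not say which visit feeds the differential R-squared models, the baseline question could also be answered with data altered by training.

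**Working it through.** **Step 1: what each analysis can contrast.**

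- Section 9.4.8, first paragraph: strength against volume within an anticipation condition. No arm, volume load, visit or interaction is named.
- Section 9.4.8, second paragraph: B coefficients by visit. No arm contrast is stated. The first paragraph sets such coefficients aside: "Rather than comparing the B coefficients of the neck strength and cervical muscle volume terms, which are scale-dependent".
- Section 9.4.2: the only mixed model of log(net head acceleration) that is specified. It has volume load and exercise group but no cervical attributes. A group main effect would not test whether the weighting of strength and volume differs by arm.
- Section 9.4.6: the only planned interactions are with sex.

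No section gives an arm-by-strength or arm-by-volume term, or a between-arm comparison of differential R-squared.

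**Step 2: the plan's own figure.** Section 9.2 powers AIM 1 only. With 30 per arm and a slope effect of .6 × 1.25 = .75, power is Φ(.75 × √15 − 1.96) = Φ(.945) = .83, which reproduces the stated value. No precision is given for AIM 2.

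**Step 3: can a model without arm see the effect?** This illustration uses assumed values: standardised predictors correlated .6, residual SD .8 (variance .64), equal arms. The differential R-squared of a predictor with coefficient b is b²(1 − .6²)/Var(Y) = .64b²/Var(Y).

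- Both arms weight equally (−.3, −.3): Var(Y) = .09 + .09 + 2(.09)(.6) + .64 = .928. Each attribute gets .64 × .09/.928 = .062.
- Opposite weighting, control (−.1, −.5) and trained (−.5, −.1): within each arm Var(Y) = .01 + .25 + 2(.05)(.6) + .64 = .96. In controls, strength gets .64 × .01/.96 = .007 and volume .64 × .25/.96 = .167; in the trained arm these are reversed. Pooled, the coefficients average to (−.3, −.3), so each attribute gets .64 × .09/.96 = .060.

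A simulation with 200,000 records agrees: pooled .063/.061 in the first case and .059/.060 in the second, with arm-specific values .006/.168 and .167/.006. A complete reversal between arms is almost invisible when arms are pooled.

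**Step 4: how precise a between-arm analysis would be.** The full-model R-squared cancels, so the strength-minus-volume differential is r_S² − r_V², where r_S and r_V are the correlations with head acceleration.

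Inputs: r_S of .5 to .6 and r_V of .6 to .68, inside the ranges Section 2.2 reports from earlier work (.42 to .60 for strength; .60 to .76 for neck circumference, used here in place of volume). The strength–volume correlation (.5 to .7) and the visit-to-visit correlation ρ (.5 to .9) are assumptions; the documents give neither.

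Monte Carlo on trivariate normal data gives an SE of about .08 to .10 with 72 athletes and SE₃₀ of .12 to .16 with 30. For the between-arm difference in change, SE ≈ √[2 × 2 × SE₃₀² × (1 − ρ²)] = 2 × SE₃₀ × √(1 − ρ²).

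| ρ | Formula | Monte Carlo |
|---|---|---|
| .5 | 2 × (.12 to .16) × .866 = .21 to .28 | .21 to .28 |
| .8 | 2 × (.12 to .16) × .600 = .14 to .19 | .15 to .19 |
| .9 | 2 × (.12 to .16) × .436 = .10 to .14 | .11 to .14 |

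A 95% interval would exclude zero only for an observed shift of about 1.96 × .11 = .22 to 1.96 × .28 = .55 in R-squared. If strength and volume correlate .9, the SEs fall to about .05 (72 athletes) and .07 to .14 (between-arm change).

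**The case against.** A reader might infer three stronger things, and the documents do not support them.

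- *That the Section 3 question cannot be answered.* The trial randomises to two arms and schedules strength, an estimate of muscle volume and head acceleration at all four assessments (Sections 1.3, 6.2 and 8.1). The contrast is unspecified, not impossible.
- *That the Section 9.4.8 mixed models lack an arm term.* Their terms are not listed. The second paragraph looks like the intended route to the Section 3 question and may inherit group and volume load from Section 9.4.2. What can be said is that no arm contrast is stated.
- *That four rows per athlete will be pooled as if independent.* The text does not say that all visits enter the differential R-squared models, and it resamples subjects, so the intervals would respect clustering within athlete. Only a mixing of between- and within-athlete associations would remain, and only if visits were in fact pooled.

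Other points count as well. The written decision rule compares strength with volume and does not claim that exercise shifted anything. The Section 3 justification column already holds both questions, so the wordings are partly reconciled. AIM 2 is exploratory. The SEs above rest on assumed correlations and show that the better analysis would be imprecise, not that the plan is biased. Restricting Section 3 to baseline would be the sponsor's choice, not a necessary correction.

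All of this stands. It narrows the point but does not supply the missing contrast or say which of the two questions is AIM 2.

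**Conclusion.** The point holds in a limited form. AIM 2 carries two different objectives, and no section states the between-arm contrast that the Section 3 version requires. The stated route is differential R-squared without arm or visit, followed by coefficients that the same section calls scale-dependent, compared over time. It could not separate an exercise effect from growth and general training. The pooling illustration depends on assumed coefficients and shows what can happen, not what will. The SE of .11 to .28 for the between-arm change depends on the assumed strength–volume and visit-to-visit correlations and is smaller if strength and volume are more tightly correlated. The consequence is confined to an exploratory aim; the primary and secondary analyses are untouched.

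**What to change.** 1. Reconcile the AIM 2 wording in Sections 1.1, 2.2 and 3, keeping one question or labelling both.
2. State in Section 9.4.8 that the baseline question is answered at Time Point 1, one row per athlete, for each loading and anticipation condition.
3. If the exercise question is kept, compute the strength-minus-volume differential R-squared in each arm at Time Points 1 and 4. Report the between-arm difference in change with a bootstrap interval, resampling athletes within arm. Use this in place of the comparison of B coefficients over time.
4. Report the result as exploratory, and make no claim from pooled-arm results that exercise altered relative influence.

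The cost is a few sentences and a small bootstrap on data already scheduled for collection. The drawback is that the plan must acknowledge how imprecise the between-arm estimate will be.
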